4.6 Time Commitment for Participants (Aim 1)

On average, we anticipate that participants will take about 6 weeks to complete the study from consent to post-treatment assessment. Baseline and post-treatment surveys will take approximately 30-45 minutes to complete. We expect that consent will occur no more than 2 weeks prior to the initiation of the first intervention session, although participants can begin participation in the intervention as soon as both members of the couple complete the baseline survey. The intervention sessions are intended to be delivered at weekly intervals, however, realizing that patient and partner health or other circumstances may arise that can delay sessions, we will allow for the four sessions to be completed within 12 weeks (from the start of the first session). Completion of the post-treatment survey by both members of the couple should occur 2-7 days after completing the last intervention session (but if they need more time to complete it, we will allow this). Thus, the minimum study duration would be approximately 5 weeks, and the maximum study duration would be approximately 14 weeks.

4.7 Developmental Survey (Aim 2) Procedures

Eligible patients who refuse the pilot trial will be given the opportunity to participate in the research (Aim 2) by engaging in a brief telephone survey (or in-person, or over the web, depending on the method of recruitment) assessing their reasons for not participating and preferences for interventions addressing sexual concerns (See Developmental Aim Draft Survey in Appendix).

The administration of this survey will likely occur at the time of screening but may occur at a later time if necessary (but no later than one month post-screening, if a patient is willing but unable to complete the survey at the time of screening). This survey will be administered only once and contains 8 items. Questions assess patients' reasons for non-participation in the intervention study, about intervention preferences, and about preferences for resources, as well as two questions on race/ethnicity. If administered through the web, the recruiter will send the patient a link for completing the online survey and the items will be identical regardless of the format.

Patients will be asked the survey questions privately; if necessary, partners will be asked to leave the room to ensure patient privacy. This is particularly important because one item specifically asks whether the patient would like the partner included in programs. If the patient does not want to be interviewed alone, we will not proceed.

The time commitment for participants in Aim 2 is approximately 10 minutes.

5.0 Risks to Participants

The major risks for study subjects are (1) discomfort at answering study questions during the focus group, on surveys, or during intervention sessions and (2) loss of privacy or confidentiality. Due to the protections we will have in place, we believe these risks to be minimal. Additionally, there is some risk that couples in Aim 1 who are distressed may

experience additional distress during intervention discussions about sensitive topics. Based on our previous experience with couple-based interventions, we expect this risk to be minimal.

We are concerned with ensuring that study questions pertaining to sexuality are handled in a sensitive manner. We have chosen standardized sexuality assessment tools that have been widely used and validated to every extent possible, and have made every attempt to ensure that the sexuality items used in the current study are minimally intrusive and appropriate. If patients do not want to answer the screening question assessing their degree of sexual concerns or discuss this topic further, they may choose not to answer this question and not to participate in the study. They will also be informed as to the nature of the items in the study that will be asked of them, and will be assured in the consent forms that they do not have to answer any questions that make them uncomfortable. We will make it clear that whether or not they answer the screening items or agree to participate in the research study will not affect their care.

6.0 Potential Benefits to Participants

While we hope that the Intimacy Enhancement intervention will benefit patients and partners, there may be no direct benefit to the study participants. It is possible that the Intimacy Enhancement intervention may address patients' sexual concerns and therefore have a beneficial effect on patient and partner sexual quality of life outcomes, relationship outcomes, and on patient psychosocial outcomes. Couples in the Educational Control condition may also benefit from having the support of a professional for an equivalent length of time and from the educational material provided. Findings from the pilot trial will inform the design of a larger multi-site trial which has the potential to improve patient health and quality of life, once disseminated. Findings from the developmental aim may inform future research on interventions that may be well-suited to addressing the sexual concerns of a large number of breast cancer survivors. The minimal risks to subjects are reasonable in relation to potential benefit in improving the health and quality of life of women with breast cancer, especially in light of the dearth of available evidence-based interventions addressing sexual concerns for this population.

7.0 Provisions to Maintain the Confidentiality of Data

7.1. General Provisions to Maintain the Confidentiality of Data

In order to minimize the risks associated with discomfort in answering questions, participants will be told that they do not have to answer any research questions and that, if they change their mind about participating, they can stop at any time. All information collected for this study will be kept confidential. Subjects will be told that all information will be kept in strict confidence. All patient discussions about the study and training sessions will occur in private areas or over the telephone.

In order to minimize the risks associated with loss of confidentiality, all patient data (including audio recordings of intervention sessions) will be kept confidential and secure, will be de-identified for analytic purposes, and none of the patients' information will be released to their physician, health care organization, or any other third party without the patient's permission, except as required by law. All computer files with patient or provider data will be password protected with access restricted to study investigators, and all data forms will be kept in locked cabinets. The file that links subject names to identifying numbers will not be kept with the data, and will not leave the institution.

We will use RedCap to capture patient/partner outcome data, which is a secure, web-based application that supports easy data manipulation with audit trails and reporting capabilities, including automated export to SPSS (which we will use to maintain outcome data, in a de-identified data set), which we will use. Data that are exported to SPSS are de-identified. REDCap was developed around HIPAA-Security guidelines, and all web-based information transmissions are encrypted. All data will be stored on a server maintained by the FCCC Information Systems and Technology Department in a secure data center. The server is backed up to tape on a daily basis and is protected from inappropriate outside access by commercial grade firewalls.

All audio recordings of intervention sessions will be destroyed when the study is complete. RedCap data storage is HIPAA-compliant with efforts to keep patient data confidential; data that are exported from RedCap for analytic purposes are de-identified prior to export.

8.0 Costs to Participants

There are no costs to participants for their participation in the study.

9.0 Consent Process

9.1. Overview of Consent Processes

If a participant consents to participate in Aim 1, the couple-based intervention study, they are consenting to completing survey data online about their physical, sexual, and emotional health, to allow us to obtain limited medical data from their medical records, and to participating in telephone sessions with their partners that either address intimacy concerns or that deal with healthy living topics, as well as completing surveys about their participation in the interventions.

Those who participate in Aim 2 are consenting to providing information about their reasons for lack of participation and intervention preferences on a brief survey interview.

9.1.1. Consent Process for Aim 1

First, the recruiter or study team member will engage in a discussion with candidates (both patients and partners) with respect to the study procedures, risks, and benefits. This will generally occur during the screening process. Once candidates indicate their intent to participate and an adequate understanding of the study procedures, as judged by the recruiter, the recruiter will give them instructions regarding how to consent using the web-based consent process and for completing the consent and surveys. They will be given the chance to ask questions during these verbal conversations, as well as the PI's information should they require it before moving to the next step in this process.

Next, as mentioned above, patients and partners will be sent a link (one for patients, one for partners) which they will use at home in order to complete the consent process. Completion of the consent is necessary prior to having access to the online survey. The consent form also contains a question in which the participant can indicate that he or she is willing or not willing to be contacted directly about similar studies in the future. It is clear that the participant can participate in the current study regardless of his/her response to this item.

If patients and/or partners are unable to complete the consent process online, they will be given the option to complete a written consent form either through the mail or in person. If necessary, we will send self-addressed stamped return envelopes for the return of these consents along with paper and pencil surveys (if necessary), and will return signed copies to the couple.

In order to reduce the likelihood that web-based survey completion will lead to attrition, as can occur when the consent process takes place outside of an in-person clinic situation, the study team will engage in several reminder calls to the patient and/or partner to assist with completion (approximately 3 but no more than 6). These may include phone calls by the PI or recruiter, and email reminders, as well as attempting to set up an "appointment" with the patient and/or partner for consent and survey completion. Once the reminders have reached the maximum, we will cease to contact the patient or partner about the study and will note this in our files.

Once both members of the couple have completed consent, the couple is considered to be enrolled. If only one member of the couple completes consent and the other decides not to participate, this couple is not enrolled because only couples can participate in this intervention study.

Only English speaking patients will be enrolled. Children will not be enrolled in this study.

9.1.2 Consent Process for Aim 2

After screening and refusal of the pilot trial, as documented on the patient screening script, using a brief IRB-approved oral consent process by a recruiter/research coordinator, the participant will be given information about the voluntary nature of the study, their ability to stop at any time, and study risks and benefits (see Developmental Aim Consent Script in Appendix).

For the following reasons, we have submitted a Request for Waiver of Documentation of Informed Consent form 45 CFR 46.117(c)(1)(2): 1) The research is not subject to FDA regulations; 2) the research involves no more than minimal risk or harm to participants; and 3) the research involves no procedures for which written consent is normally required outside of a research setting.

Patients who agree to this brief study will be given a written print-out of the written oral consent document (distinguished from the oral consent script), either in person, if they are recruited in person, or they will be sent this through the mail if they have been recruited over the telephone. Oral consent will be obtained irrespective of the method of recruiting. The person obtaining the consent shall sign and date the consent script as a record that the oral consent discussion occurred.

10.0 Off-Study Criteria

Any participant may leave the study at any time due to distress or other reasons. We do not have a priori reasons for letting participants off the study. An exception would be if a patient or partner experiences significant psychological or marital distress during the study such that it is deemed detrimental for them to continue in our study at the expense of receiving psychological or mental health services. If this happens, we will follow the procedures listed below for Adverse Event reporting, and will recommend that the couple not continue in this study but rather receive appropriate referrals, as described below in section 15.0. We will track such events, as described below, and we expect them to be extremely rare.

In the case of attrition after randomization to either intervention, the participant and his or her partner may be asked if they would be willing to remain in the study for data collection in four weeks which will enable us to conduct intent-to-treat analyses (or the length of time that would coincide with the end of their treatment sessions).

If a patient's disease recurs or needs to start active treatment during the study, they will be allowed to remain on the study, if they choose, and this information will be tracked in their research files pertaining to their medical records. Because the duration of the study involvement is relatively brief, we expect these circumstances to be infrequent.

11.0 Drugs and Devices

Not applicable.

12.0 Multi-Site Research Study

Not applicable.

13.0 Statistical Analysis

13.1. Statistical Analyses for Aim 1

13.1.1. Primary and Secondary Outcome Variables

13.1.1.1. Primary outcomes are feasibility and acceptability of the study. Feasibility will be measured through study accrual, attrition, and session completion. Acceptability is measured using the CSQ-8 (See Self-report Materials in Appendix).

13.1.1.2. Secondary outcomes are preliminary efficacy of the study in patient and partner sexual outcomes (sexual function, sexual satisfaction and intimacy, sexual distress), patient and partner relationship outcomes (emotional intimacy, sexual communication, relationship quality), and patient psychosocial outcomes (body image distress, psychological distress). The measures assessing these outcomes can be found in Table 3 above.

13.1.2. Analyses

13.1.2.1. Feasibility. Analyses will be descriptive. We aim for accrual at a rate of 30% to match our prior study,⁴² but a rate over 20% will be acceptable. Attrition at levels greater than those found by similar studies⁴⁷ (e.g., 30%) will be considered unfeasible. 80% of participants completing the 4 sessions is considered adequate.

13.1.2.2. Acceptability. Analyses will be descriptive. Adequate acceptability of the study will be indicated by a group median score ≥ 28 on the CSQ-8,⁷⁶ representing a fairly high score across a range of studies, including a behavioral marital therapy randomized controlled trial.⁷⁷

13.1.2.3. Preliminary efficacy. Preliminary efficacy of the IE intervention on patient and partner sexual outcomes, patient and partner relationship outcomes, and patient psychosocial outcomes will be established using an effect size calculation method that is appropriate for small sample sizes³⁴ that our team has employed previously.^{34,49} First, pre-post changes scores are calculated for each participant. Second, the between-group effect size is calculated by subtracting the mean control group change score from the mean IE group change score. This difference is then divided by the standard deviation of the pooled change score. Given that multilevel dyadic analyses are questionable in small sample sizes,⁷⁸ we will consider dyadic analyses, including actor-partner effects,⁷⁹ in the planned R01.

Because our primary goal through the analyses for this aim is to generate effect sizes for a larger planned study, we will conduct the analyses described above using data from study completers. However, we will also attempt to obtain post-treatment surveys even for couples who have dropped out of the study during the intervention phase, to allow us to conduct intent-to-treat analyses. Patients without any post-treatment data will have baseline data used in these analyses.

13.2. Statistical Analyses for Aim 2

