3.2 Preliminary Studies

Previously, the PI conducted a small uncontrolled pilot study examining a telephone-based IE intervention in 14 couples facing colorectal cancer (9 completed; Study 1 in Table 1).⁴¹ This intervention aimed to improve patient and partner skills in coping with sexual concerns related to colorectal cancer and improve physical and emotional intimacy. Findings showed moderate to large effects for most sexual and relationship outcomes. [name] then compared the intervention to a wait list control in a randomized study in 23 couples (18 completed; Study 2 in Table 1).⁴² Findings showed strong positive effects on all outcomes for partners and on sexual function and self-efficacy for patients. Importantly, across both of these studies the **vast majority of participants (>75%) reported liking the telephone-based format**; qualitative responses indicated that this format was appreciated for both its convenience and comfort in discussing sensitive topics.

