4.4 Study Data Collection and Measures

4.4.1 Medical Data Collection (Aim 1)

Because patient self-report about medical history can occasionally differ from the data on the same items in patients' charts (e.g., treatments received), we will collect the following data on enrolled patients through medical chart review: date of diagnosis and disease stage, dates and types of treatments and surgeries received for breast cancer, current treatment status, current medication use (including endocrine therapies), and current menopausal status (See Medical Records Data Collection Form in Appendix). The data abstraction will be performed by [name], a Nurse Practitioner and Co-Investigator on our study, or another member of the study team trained or supervised by [name], and entered into our de-identified databases. This medical chart review is documented in the consent form.

4.4.2 Self-Report Data Collection (Aim 1). An overview of study measures and collection time points for participants in Aim 1 (the pilot trial), including number of items in each scale, is in **Table 3**. After consenting, patients and partners will complete pre- and post-intervention outcome measures through a web portal on their home computers using RedCap.

4.4.2.1 Overview of Self-Report Data Collection (Aim 1).

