Beliefs (self-efficacy) ^{64,65}	Self-efficacy	3	X					X
Intimate Activities and Use of Sexual Aids (PROMIS Items) ^{27,61*}	Frequency of sexual activity/use of aids	8	X					X
Patient and Partner Relationship Outcomes								
PAIR Emotional Intimacy Scale ⁶³	Emotional Intimacy	6	X					X
Dyadic Sexual Communication Scale (DSCS) ⁶⁶	Sexual communication	13	X					X
Dyadic Adjustment Scale-7 item (DAS-7)	Relationship quality	7	X					X
Patient Psychosocial Outcomes – ONLY COMPLETED BY PATIENT								
Body Image Scale (BIS) ⁶⁷	Body image distress	10	X					X
Patient Health Questionnaire-9 item (PHQ-9) ⁶⁸	Distress (depression)	9	X					X
Generalized Anxiety Disorder 7-item (GAD-7) ⁶⁹	Distress (anxiety)	7	X					X
Additional Items Completed by Patients/Partners								
Baseline demographic information for patient/partner	Demographic data	12/7	X					
Post-treatment demographic items	Demographic data	2						X
Charlson Comorbidity Index ⁵⁵	Medical comorbidity	11	X					
Impact of Events Scale ⁵²	Cancer-Specific Distress	22	X					X
Sexual Self-View (importance of sexuality to self)	Sexual self-view	2	X					X
Total # of items in baseline scales								
Patients	153							
Partners	95							
Intervention Process Forms (completed individually)								
Program Evaluation Form	Credibility	7		X				
Materials Review Form	Adherence	7			X	X	X	
CSQ-8 ⁵⁷	Acceptability	8						X
Additional Acceptability Questions ^{64,65}	Acceptability	18						X
Skills Assessment ^{**64,65}	Utilization of skills	3						X
Additional Information Completed by Patients								
Post-treatment demographic information	Demographic/medical data	2						X
Total # of items in post-treatment scales								
Patients	169							

Partners	118							
* indicates that patients only complete this measure ** indicates that only IE participants complete this measure								

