13.2.4. Sample Size Calculations

The objective of this study is to pilot test the newly adapted Intimacy Enhancement study and to allow us to calculate effect sizes that will inform a larger R01 trial that is expected to follow from this study. We selected 30 couples to participate in this trial because it is a large enough sample to provide ample pilot data while maintaining adequate feasibility in the time allotted. Further, we have chosen a 2:1 allocation to the Intimacy Enhancement condition, which allows us to gather greater information from participants in this condition, our primary interest, relative to the Couple Education condition.

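### Section 13.1.2.3 plans a change-score effect size with no baseline adjustment, no confidence interval and an ambiguous SD, although its stated purpose is to supply effect sizes for the R01

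*Combined protocol and SAP*

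**What the plan says.** Section 13.1.2.3 takes each participant's pre-post change and states that "the between-group effect size is calculated by subtracting the mean control group change score from the mean IE group change score". The next sentence reads: "This difference is then divided by the standard deviation of the pooled change score". No baseline covariate, standard error or confidence interval is named there or elsewhere in the document.

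Baseline data exist: under section 4.4.2, "patients and partners will complete pre- and post-intervention outcome measures through a web portal". Some scales go to patients only; the asterisk in Table 3 "indicates that patients only complete this measure".

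Efficacy is a secondary outcome (section 13.1.1.2). Even so, section 13.1.2.3 states that "our primary goal through the analyses for this aim is to generate effect sizes for a larger planned study", and section 13.2.4 says the trial is meant "to allow us to calculate effect sizes that will inform a larger R01 trial". The main analysis uses completers. An intent-to-treat analysis is also foreseen, in which patients with no post-treatment data have their baseline values used.

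**The concern.** Effect sizes from this trial will be carried into the planning of a larger one. With about 30 couples at 2:1, each is very imprecise. A point value with no interval hides that, and a planner could take 0.5 at face value when the data allow anything from mild harm to a very large benefit.

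Two further matters bear on what the R01 can use. First, the plan collects a baseline score on the same scale and uses it only by subtraction, which is usually less efficient than regression on it. Second, a d in change-SD units depends on the pre-post correlation, which the plan does not report, and its divisor may be the SD pooled within arms or the SD over all change scores together.

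**Working it through.** **Inputs.** 30 couples (sections 4.1 and 13.2.4) at 2:1 (section 4.5.1) give 20 vs 10. The 30% attrition level in section 13.1.2.1, applied equally to both arms, gives 14 vs 7. Section 13.2.4 justifies the sample size by feasibility, so there is no power or precision figure to reproduce. The pre-post correlation ρ and the SDs are not given; the values below are assumptions. Write k = 1/n1 + 1/n0, N = n1 + n0 and q = post SD / pre SD.

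**1. The interval that would not be shown.** t = d/√k, with limits from the noncentral t distribution on N − 2 df.
- 20 vs 10: k = 0.15, t = 0.5/0.387 = 1.29, df 28. The 95% CI for d = 0.5 is about -0.27 to 1.27.
- 14 vs 7: k = 0.2143, t = 0.5/0.463 = 1.08, df 19. The 95% CI is -0.43 to 1.41.

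**2. Change score against ANCOVA, equal SDs (q = 1).** In baseline-SD units:
- Var(change) = 2(1 − ρ)k
- Var(ANCOVA) = (1 − ρ²)k(N − 3)/(N − 4), where the last factor is the cost of estimating the slope.

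For example, at 20 vs 10 and ρ = 0.5: change 0.150, SE 0.387; ANCOVA 0.75 × 0.15 × 27/26 = 0.1168, SE 0.342. The reduction is 11.7%.

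| ρ | SE change, 20 vs 10 | SE ANCOVA | Reduction | Reduction, 14 vs 7 |
|---|---|---|---|---|
| 0.3 | 0.458 | 0.376 | 17.8% | 17.0% |
| 0.5 | 0.387 | 0.342 | 11.7% | 10.9% |
| 0.7 | 0.300 | 0.282 | 6.0% | 5.1% |
| 0.9 | 0.173 | 0.172 | 0.7% | -0.3% |

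Break-even is ρ = 2(N − 4)/(N − 3) − 1: 52/27 − 1 = 0.926 at N = 30 and 34/18 − 1 = 0.889 at N = 21. Simulation (40,000 trials per setting) agrees. The 95% half-widths at 20 vs 10 and ρ = 0.5 are 0.79 (change) and 0.70 (ANCOVA), so the interval is wide either way.

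**3. Unequal SDs.** In general Var(change) = (1 + q² − 2ρq)k and Var(ANCOVA) = q²(1 − ρ²)k(N − 3)/(N − 4). Reduction in SE from ANCOVA at 20 vs 10:

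| q | ρ 0.5 | ρ 0.7 | Change score more precise for ρ of about |
|---|---|---|---|
| 1.0 | 11.7% | 6.0% | above 0.93 |
| 1.1 | 7.9% | 2.2% | 0.79 to 0.96 |
| 1.25 | 3.7% | -0.9% | 0.65 to 0.89 |

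The loss is bounded. Since (1 + q² − 2ρq) − q²(1 − ρ²) = (1 − ρq)² ≥ 0, the variance ratio of ANCOVA to change score cannot exceed (N − 3)/(N − 4). The excess is at most 1/26 = 3.8% at N = 30 and 1/17 = 5.9% at N = 21.

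**4. The divisor.** The SD over all change scores, relative to the SD within arms, is √{[(N − 2) + (n1·n0/N)d²]/(N − 1)}. At 20 vs 10, n1·n0/N = 6.67. At d = 0.5 this is √(29.67/29) = 1.011, so d falls by 1.1%; at d = 1.0 it is √(34.67/29) = 1.093, a fall of 8.5%. At 1.15, 1.29 and 1.75 the falls are 11%, 14% and 23%. Values of that size appear in the effect-size table of the background section; the first two come from the uncontrolled pilot, so they indicate scale only.

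**5. Dependence of d on ρ.** With equal SDs, d = 0.5 in change-SD units is 0.5√[2(1 − ρ)] baseline SDs: 0.59 at ρ = 0.3 and 0.22 at ρ = 0.9.

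**6. Filling with baseline.** Simulated ANCOVA at 20 vs 10, 30% of post scores replaced by baseline at random, ρ = 0.6, equal SDs: at a true effect of 0.5 SD the mean 95% half-width was about 0.58, against 0.79 using observed data only. Coverage of the true effect was about 92% to 93%, and about 86% to 87% at a true effect of 1.0 SD.

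**The case against.** The best defence is that this is a pilot sized for feasibility, efficacy is secondary, and the plan gives a reason for its method: it suits small samples and the team has used it before. The estimate is valid, and a reader could rebuild an interval from d and the arm sizes once the SD is defined. This limits the seriousness of the point but does not remove it. One covariate costs one degree of freedom, and the plan's explicit small-sample caution concerns multilevel dyadic models, which are not requested here. Comparability with the earlier pilots is met by keeping the planned d.

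Three stronger readings are tempting but not supported.
- **That the change-score difference is biased.** Under randomisation it is not.
- **That ANCOVA wins unless the correlation is about 0.9.** That needs equal pre and post SDs. Patients must score 3 or more on a sexual-concerns item to enter (section 4.3), so a restricted baseline SD is plausible, and the break-even could be well below 0.9.
- **That the earlier pilot proves the harm.** Section 3.2 describes "a randomized study in 23 couples (18 completed; Study 2 in Table 1") and says "Findings showed strong positive effects on all outcomes for partners" without intervals. It is a background summary, and it does not show that the publication reported none. For the partner intimacy value of 0.51, a 95% CI would be about -0.44 to 1.44 at 9 vs 9 or -0.49 to 1.50 at 12 vs 6. The arm split, the effect-size definition and the analysed set are not stated, so this is illustration only.

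**Conclusion.** The point holds as a matter of precision and reporting, and the change should be made. The missing interval is the weightier part: at the planned size an effect of 0.5 is compatible with values from below zero to above 1.2, whichever estimator is used. Baseline adjustment is a cheap improvement, worth roughly 6% to 18% of the SE for correlations of 0.3 to 0.7 if pre and post SDs are equal, and less if the post SD is larger. In the unfavourable cases it costs almost nothing. The SD wording is minor for d up to about 1 and material above that. All the ANCOVA figures rest on assumed correlations and SD ratios, and those at 14 vs 7 on attrition falling equally on both arms.

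**What to change.** In section 13.1.2.3, for each efficacy scale measured before and after treatment, in patients and in partners where they complete it:
- Regress the post-treatment score on arm and the same scale's baseline score, in those with observed post-treatment data.
- Report the adjusted difference with a 95% CI, in raw units and standardised by the pooled baseline SD.
- Report the pre and post SDs, the pre-post correlation and the residual SD, so that the R01 can be planned under either analysis.
- Keep the change-score d for comparison with the earlier pilots, divided by the pooled within-group SD of change, with its 95% CI.
- State that these intervals apply to observed post-treatment data, because an ordinary interval computed after filling missing post scores with baseline values can be too narrow.

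The cost is a few sentences of plan text, a few lines of code, one degree of freedom per model and a trivial loss of precision where the correlation is high. No new data are needed.
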